### 11.2.3. Demography

- Age of mother: Age at the reference activity, computed as the number of units between the date of birth and the reference activity. Note that due to incomplete date, the derived age may be incorrect by 1 month when month is missing from the birthdate. This may lead to apparent inconsistency between the derived age and the eligibility criteria/the age category used for randomization. Gestational age at delivery : The gestational age at delivery is calculated by adding the number of weeks between screening and delivery to the gestational age recorded at the ultrasound screening.
- Gestational age at dose 1: The gestational age at dose 1 is calculated by adding the number of weeks between screening and dose1 to the gestational age recorded at the ultrasound screening.
- Age of infant: Age at the reference activity, computed as the number of complete weeks between the date of birth and the reference activity.
- Conversion of weight to kg: the following conversion rule is used:

Weight in Kilogram= weight in Pounds / 2.2 + weight in ounces / 35.2

The result is rounded to 2 decimals.

- Conversion of height to cm: the following conversion rule is used:  
Height in Centimetres = Height in Feet \* 30.48 +  
Height in Inch \* 2.54  
The result is rounded to the unit (ie no decimal).
- Conversion of temperature to °C: the following conversion rule is used:  
Temperature in °Celsius = ((Temperature in °Fahrenheit -32) \*5)/9  
The result is rounded to 1 decimal.

#### 11.2.4. Immunogenicity

- For a given subject and given immunogenicity measurement, missing or non-evaluatable measurements will not be replaced.
- The Geometric Mean Concentrations (GMCs) calculations are performed by taking the anti-log of the mean of the log titre transformations. Antibody concentrations below the cut-off of the assay will be given an arbitrary value of half the cut-off of the assay for the purpose of GMC calculation.
- A seronegative subject is a subject whose antibody concentration is below the assay cut-off value. A seropositive subject is a subject whose antibody concentration is greater than or equal to the assay cut-off value.

Vaccine response definition:

- Vaccine response to D and T antigens was defined as:
  - for subjects with pre-vaccination concentration < 0.1 IU/mL antibody (ie below the seroprotection cut-off), antibody concentrations at least  $\geq 0.4$  IU/mL, one month after vaccination, and
  - for subjects with pre-vaccination concentration  $\geq 0.1$  IU/mL (ie equal or above the seroprotection cut-off), an increase in antibody concentrations of at least four times the pre-vaccination concentration, one month after vaccination.
- Vaccine response to PT, FHA and PRN antigens was defined as:
  - for subjects with pre-vaccination antibody concentration below the assay cut-off, post-vaccination antibody concentration  $\geq 4$  times the assay cut-off,
  - for subjects with pre-vaccination antibody concentration between the assay cut-off and below 4 times the assay cut-off, post-vaccination antibody concentration  $\geq 4$  times the pre-vaccination antibody concentration, and
  - for subjects with pre-vaccination antibody concentration  $\geq 4$  times the assay cut-off, post-vaccination antibody concentration  $\geq 2$  times the pre-vaccination antibody concentration.

The thresholds defining seropositivity are provided below as per new re-validated assay are the following.

**Table 4 Humoral Immunity (Antibody determination)**

System	Component	Method	Kit/Manufacturer	Unit	Cut-off†	Laboratory*
Serum	Corynebacterium diphtheriae .Diphtheria Toxoid Ab.IgG	ELI	NA	IU/ml	0.057	GSK Biologicals or designated laboratory
Serum	Clostridium tetani .Tetanus Toxoid Ab.IgG	ELI	NA	IU/ml	0.043	GSK Biologicals or designated laboratory
Serum	Bordetella pertussis .Pertussis Toxin Ab.IgG	ELI	NA	IU/ml	2.693	GSK Biologicals or designated laboratory
Serum	Bordetella pertussis .Filamentous Hemagglutinin Ab.IgG	ELI	NA	IU/ml	2.046	GSK Biologicals or designated laboratory
Serum	Bordetella pertussis .Pertactin Ab.IgG	ELI	NA	IU/ml	2.187	GSK Biologicals or designated laboratory

ELI: ELISA

NEU: Neutralisation assay

NA: Not Applicable

IU/ml: International Units per millilitre

†Assays for diphtheria, tetanus and pertussis were re-developed and re-validated as per most recent CBER recommendations (Guidance for Industry “Bioanalytical Method Validation” from September 2013). The new assay cut-offs that apply are listed in the table.

\*GSK Biologicals laboratory refers to the Clinical Laboratory Sciences (CLS) in Rixensart, Belgium and Wavre, Belgium.

- In general, the assay cut-off is the value under which there is no quantifiable result available. For an assay with a specific ‘assay cut\_off’, numerical immuno result is derived from a character field (rawres):
  - If rawres is ‘NEG’ or ‘-’ or ‘(-)’, numeric result= assay cut\_off/2,
  - if rawres is ‘POS’ or ‘+’ or ‘(+)’, numeric result = assay cut\_off,
  - if rawres is ‘< value’ and value<=assay cut\_off, numeric result =assay cut\_off/2,
  - if rawres is ‘< value’ and value>assay cut\_off, numeric result =value,
  - if rawres is ‘> value’ and value<assay cut\_off, numeric result =assay cut\_off/2,
  - if rawres is ‘> value’ and value>=assay cut\_off, numeric result =value,
  - if rawres is ‘<= value’ or ‘>= value’ and value<assay cut\_off, numeric result =assay cut\_off/2,
  - if rawres is ‘<= value’ or ‘>= value’ and value>=assay cut\_off, numeric result =value,
  - if rawres is a value < assay cut\_off, numeric result = assay cut\_off/2,
  - if rawres is a value >= assay cut\_off, numeric result = rawres,
  - else numeric result is left blank.

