5.6.1.3.4. Sampling

Refer to the Module on Biospecimen Management in the SPM for detailed instructions for the collection, handling and processing of the samples.

Blood sampling for immune response assessments

Blood samples will be taken during certain study visits as specified in Section 5.5 List of Study Procedures.

- A volume of approximately 5 mL of whole blood (to provide approximately 1.7 mL of serum) should be drawn from all subjects for each analysis of humoral immune response at Visit 1 and Visit 2. In case a woman gives birth to an infant before Visit 2, a blood sample must be collected from the subject before the cross-over vaccination is given to the subject.
- A volume of approximately 2.5mL of whole blood (to provide approximately 0.75 mL of serum) from the umbilical cord will be collected from all subjects at Visit 3.

After centrifugation, serum samples should be kept at –20°C/ –4°F or below until shipment. Refer to the SPM for more details on sample storage conditions.

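### The SAP enters `< value` and `<= value` results above the assay cut-off at the full bound and counts them as seropositive; the size of the effect is unknown and may be zero

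*SAP*

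**What the plan says.** SAP section 11.2.4 derives each numeric antibody result from a character field, using the list under Table 4. Two lines cover `< value`:

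- One begins "if rawres is ‘< value’ and value<=assay" cut-off and gives half the cut-off.
- The other begins "if rawres is ‘< value’ and value>assay" cut-off and gives the value itself.

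A `<= value` result at or above the cut-off is also entered at the value. A `> value` result below the cut-off becomes half the cut-off. The closing line, which leaves a result blank, is reached only by formats not listed before it.

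The same section says "A seropositive subject is a subject whose antibody concentration is greater than or equal to the assay cut-off value". For the GMC, a concentration below the cut-off "will be given an arbitrary value of half the cut-off of the assay for the purpose of GMC calculation". The list describes the cut-off by saying that "the assay cut-off is the value under which there is no quantifiable result available".

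Nothing in the protocol or SAP flags `< value` results above the cut-off as censored, treats them as non-evaluable, counts them or plans a sensitivity analysis for them.

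**The concern.** A result reported as `< v` says that the concentration is below v, so v is a number the sample is known not to have. Entering v uses the bound as data. Because v exceeds the cut-off, the sample is seropositive by definition, even if the true concentration is under the cut-off.

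Three sets of endpoints use these numbers: the primary cord-blood GMCs for PT, FHA and PRN; cord seropositivity; and maternal seropositivity, seroprotection and vaccine response. Anti-PT has the least room on the primary criterion. The protocol assumes a true ratio of 2.3 against a required lower limit of 1.5, and all three antigens must meet that limit.

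**Working it through.** **The plan's own figure.** Protocol section 10.3 gives 272 evaluable per group, one-sided alpha 0.025, anti-PT log10 SD 0.577, true ratio 2.3 and null ratio 1.5.

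- Difference: log10(2.3/1.5) = 0.1856.
- Standard error: 0.577 × √(2/272) = 0.0495.
- Power: Φ(0.1856/0.0495 − 1.96) = 96.3%, against the stated 96%.

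The sample size is reproduced and is not in question here.

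**What the rules do.** For anti-PT the SAP cut-off is 2.693 IU/mL:

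| Raw result | Entered as | Status |
|---|---|---|
| `<2.693` | 1.3465 | seronegative |
| `<2.72` | 2.72 | seropositive |
| `<5.386` | 5.386 | seropositive |
| `<26.93` | 26.93 | seropositive |

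As the bound crosses the cut-off, the entered number jumps from 0.5 to just over 1 times the cut-off. The other four antigens follow the same pattern. For anti-D and anti-T, a bound of 0.1 IU/mL or more also counts as seroprotected; for example, anti-D `<0.228` is entered as 0.228.

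**Vaccine response.** Suppose a pre-vaccination anti-PT result is `<20`. It is entered as 20, which exceeds 4 × 2.693 = 10.772, so response requires 2 × 20 = 40 IU/mL. If the woman is truly seronegative, she should need only 10.772. An overstated pre-vaccination value can thus lower the response rate, and an overstated post-vaccination value can raise it.

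**GMC, outer case.** The documents give no frequency, so f and m below are assumptions. Let a fraction f of one arm be reported as `< m × cut-off`, and let every such sample truly be below the cut-off. Relative to half the cut-off, the rule multiplies that arm's GMC by (2m)^f. Starting from a ratio of 2.3:

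| f | m | GMC multiplier | Ratio if all Control | Ratio if all dTpa | Power if all Control (SD held) |
|---|---|---|---|---|---|
| 1% | 2 | 1.014 | 2.27 | 2.33 | 95% |
| 1% | 10 | 1.030 | 2.23 | 2.37 | 94% |
| 5% | 2 | 1.072 | 2.15 | 2.47 | 88% |
| 5% | 10 | 1.162 | 1.98 | 2.67 | 68% |
| 10% | 2 | 1.149 | 2.00 | 2.64 | 72% |
| 10% | 10 | 1.349 | 1.70 | 3.10 | 20% |

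If f and m are equal in both arms, the multipliers cancel and the ratio stays at 2.3.

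**GMC, against a mild alternative.** If value/2 is entered instead of value, the arm's GMC differs by only 2^f, whatever the bound: 2^0.01 = 1.007, 2^0.05 = 1.035, 2^0.10 = 1.072.

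**Seropositivity.** For upper-bound results the overstatement in the affected arm is at most f, reached only if every such sample is truly below the cut-off. As an illustration, assume a true rate of 80% with 5% of samples affected, all truly negative:

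- The SAP rule reports 85.0%.
- Dropping the affected samples reports 80/95 = 84.2%, so most of the overstatement remains.
- Counting them all negative, then all positive, gives 80.0% to 85.0%, which contains the truth.

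**The case against.** The strongest reply is that these lines may never be used. They sit in an annex of standard derivations that also handles results coded only as positive or negative, whereas the five assays here are ELISAs with numeric units. Nothing says that the laboratory reports `< value` above the cut-off. The `> value` line needs a lower bound reported beneath the limit of quantification, which is unlikely. All of this stands as a limit on size. It does not make the rule right when it is triggered.

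Four stronger readings are tempting, and the documents do not support them:

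- A reader might infer that the primary ratio is pulled toward 1, because low concentrations are expected mainly in Control. That is plausible but not stated, and the direction depends on which arm is affected. If it is Control, the cost is power and not a false claim of superiority.
- A reader might link the small cord sample ("to provide approximately 0.75 mL of serum") to raised reporting limits. Protocol section 5.6.1.3.4 says nothing about dilution or reporting limits, and section 5.7.4.1 handles insufficient volume by testing in priority order.
- A reader might say that the rule contradicts the half-cut-off substitution. That substitution covers concentrations below the cut-off, and a `< value` result above it is not known to be there. The fault is treating a bound as exact.
- The large multipliers in the table might be read as the gain from a simple correction. They compare with half the cut-off and assume every affected sample is truly below it; against value/2 the change is 2^f.

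SAP section 7 also makes the secondary objectives descriptive, so overstated seropositivity trips no success criterion.

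**Conclusion.** The point holds as a defect in a stated rule. Whenever a `< value` result above the cut-off, or a `<= value` result at or above it, occurs, the SAP analyses an upper bound as a measurement and counts the sample as seropositive whatever its true level. The `> value` line below the cut-off makes the opposite error.

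The size is unknown and may be nil. Seropositivity error from upper-bound results is capped at f in the affected arm and can only be upward. Bias in the primary ratio may go either way and vanishes when the fraction and the bounds match across arms. The tabulated ratios and powers rest on assumed f and m, on effects confined to one arm and on an unchanged SD. They show what could happen; they do not estimate this trial. The rule is worth correcting, but it does not undermine the design or the sample size.

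**What to change.** Replace these lines in SAP section 11.2.4:

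1. Flag `< value` above the cut-off and `<= value` at or above it as upper bounds, and `> value` below the cut-off as a lower bound. Do not treat any of them as exact. The present text handles `<=` and `>=` on shared lines, so split those.
2. For the main GMC analysis, value/2 may serve as the simple substitution for upper bounds. A lower bound under the cut-off can be left non-evaluable, since the section already provides that "missing or non-evaluatable measurements will not be replaced".
3. As a sensitivity analysis, estimate the cord GMC ratio with a censored-normal likelihood on log10 concentration. Allow the variance to differ by group, in keeping with the planned unequal-variance t test.
4. Report seropositivity and vaccine response twice, with affected samples counted as all negative and then as all positive. Neither drop them nor count them all as seropositive.
5. List the number of such results by group, antigen and time point.

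The cost is a few lines of text and programming, and a slightly wider reported range if any such results occur. If the count is zero, no result changes.

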## 11.2.5. Safety analysis

### 11.2.5.1. Solicited Adverse Events

For analysis of solicited, unsolicited adverse events (such as serious adverse events or adverse events by primary MedDRA term) and for the analysis of concomitant medications, all vaccinated subjects will be considered. Subjects who did not report the event or the concomitant medication will be considered as subjects without the event or the concomitant medication respectively.

The following rules will be used for the analysis of solicited symptoms:

- Subject who didn't document the presence or absence of a solicited symptom after one dose will be considered not having that symptom after that dose in the analysis done on "administered dose"
- Subjects who documented the absence of a solicited symptom after one dose will be considered not having that symptom after that dose.
- Subjects who documented the presence of a solicited symptom and fully or partially recorded daily measurement over the solicited period will be included in the summaries at that dose and classified according to their maximum observed daily recording over the solicited period.
- Subjects who documented the presence of a solicited symptom after one dose without having recorded any daily measurement will be considered as having that symptom after that dose (at the lowest intensity).
- Intensity of the following solicited AEs will be assessed as described below.

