Handling of missing data: For a given subject and a given immunogenicity measurement, missing or non-evaluable measurements will not be replaced.

Safety/ Reactogenicity

- For the analysis of solicited symptoms, missing or non-evaluable measurements will not be replaced. Therefore the analysis of the solicited symptoms based on the TVC will include only subjects with documented safety data (i.e. symptom screen completed).
- For the analysis of unsolicited symptoms, SAEs and analyses that combine solicited and unsolicited symptoms, subjects with no report of the event will be considered to have not had the event. Subjects who do not report being administered concomitant medications and vaccinations will be considered to have not received any medications and vaccinations.

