## 6.4. Analysis of safety

### 6.4.1. Analysis of safety planned in the protocol

The primary analysis will be performed on the TVC. If in any vaccine group, 5% or more of the vaccinated subjects are eliminated from the TVC, a second analysis will be performed on the ATP cohort for analysis of safety. Analysis of safety in household contacts will be performed on the Total cohort for household contacts in Spain.

- The percentage of subjects with each specific pregnancy outcomes and listed pregnancy-related adverse events of interest/neonate-related events of interest will be tabulated with its exact 95% CI.
- The percentage of subjects with at least one local AE (solicited and unsolicited), with at least one general AE (solicited and unsolicited) and with any AE during the 8-day (Day 0–Day 7) follow-up period after the vaccination will be tabulated after each dose with exact 95% CI. The same calculations will be performed for any Grade 3 (solicited or unsolicited) symptoms, any causal relationship to vaccination and for any symptoms requiring medical attention.
- The percentage of subjects reporting each individual solicited local and general AE during the 8-day (Day 0–Day 7) follow-up period after booster vaccination will be tabulated with its exact 95% CI for each group.
- All computations mentioned above will be done for Grade  $\geq 2$  (solicited symptoms only) and Grade 3 symptoms, for symptoms considered related to vaccination (general symptoms only), for Grade 3 symptoms considered related to vaccination (general symptoms only) and for symptoms that resulted in a medically-attended visit.
- Occurrence of fever and related fever will be reported per 0.5°C cumulative temperature increments as well as the occurrence of Grade 3 fever ( $> 39.0^{\circ}\text{C}$  axillary temperature) with causal relationship to vaccination.
- Any large injection site reaction (defined as any local swelling with diameter  $> 100$  mm and/or any noticeable diffuse injection site swelling (diameter not measurable) and/or any noticeable increased circumference of the injected limb) onset within 8 days (Day 0–Day 7) after each vaccination will be described in detail.

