**Table 5 Intensity scales for solicited symptoms in adults**

Adverse Event	Intensity grade	Parameter
Pain at injection site	0	None
	1	Mild: Any pain neither interfering with nor preventing normal every day activities.
	2	Moderate: Painful when limb is moved and interferes with every day activities.
	3	Severe: Significant pain at rest. Prevents normal every day activities.
Redness at injection site		Record greatest surface diameter in mm
Swelling at injection site		Record greatest surface diameter in mm
Fever*		Record temperature in °C/°F
Headache	0	Normal
	1	Mild: Headache that is easily tolerated
	2	Moderate: Headache that interferes with normal activity
	3	Severe: Headache that prevents normal activity
Fatigue	0	Normal
	1	Mild: Fatigue that is easily tolerated
	2	Moderate: Fatigue that interferes with normal activity
	3	Severe: Fatigue that prevents normal activity
Gastrointestinal symptoms (nausea, vomiting, diarrhoea and/or abdominal pain)	0	Normal
	1	Mild: Gastrointestinal symptoms that are easily tolerated
	2	Moderate: Gastrointestinal symptoms that interfere with normal activity
	3	Severe: Gastrointestinal symptoms that prevent normal activity

\*Fever is defined as temperature  $\geq 37.5^{\circ}\text{C}$  /  $99.5^{\circ}\text{F}$  for oral, axillary or tympanic route, or  $\geq 38.0^{\circ}\text{C}$  /  $100.4^{\circ}\text{F}$  for rectal route. The preferred route for recording temperature in this study will be oral/axillary.

The maximum intensity of local injection site redness/swelling/fever will be scored at GSK Biologicals as follows:

- 0 : Absent  
 1 :  $\leq 20$  mm  
 2 :  $> 20$  mm and  $\leq 50$  mm  
 3 :  $> 50$  mm

Event	N used for deriving % per subject for Vaccination phase	N used for deriving % per dose for Vaccination phase
Concomitant vaccination	All subjects with study vaccine administered	All study visits with study vaccine administered
Solicited general symptom	Primary analysis: all subjects with study vaccine administered Sensitivity analysis: all subjects with at least one solicited general symptom documented as either present or absent (i.e., symptom screen completed)	Primary analysis: all study visits with study vaccine administered Sensitivity analysis: all study visits with study vaccine administered and with at least one solicited general symptom documented as either present or absent (i.e., symptom screen completed)

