**Reactogenicity and safety:**

- Subjects who missed reporting symptoms (solicited/unsolicited or concomitant medications) will be treated as subjects without symptoms (solicited/unsolicited or concomitant medications, respectively).

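### For individual solicited symptoms the SAP counts women with no symptom record as symptom-free, contrary to the protocol; the change is not declared, and local symptoms have no stated denominator

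*SAP*

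**What the plan says.** **Protocol.** Section 10.5 treats two cases differently. For solicited symptoms, missing measurements are not replaced, and "the analysis of the solicited symptoms based on the TVC will include only subjects with documented safety data", meaning a completed symptom screen. For events that are not solicited, including SAEs, the rule is the opposite, and it extends to the combined tables: in "analyses that combine solicited and unsolicited symptoms, subjects with no report of the event will be considered to have not had the event".

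**SAP text.** Section 11.2.5.1 opens by taking all vaccinated women for both solicited and unsolicited events: "Subjects who did not report the event or the concomitant medication will be considered as subjects without the event or the concomitant medication respectively". It then says that a woman who recorded neither presence nor absence "of a solicited symptom after one dose will be considered not having that symptom after that dose in the analysis done on" administered doses. Section 11.2.6 repeats the rule without that qualifier: "Subjects who missed reporting symptoms (solicited/unsolicited or concomitant medications) will be treated as subjects without symptoms".

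**SAP denominator table** (in 11.2.5.1, after Table 5). The solicited general symptom row reads "Primary analysis: all subjects with study vaccine administered", followed by "Sensitivity analysis: all subjects with at least one solicited general symptom documented as either present or absent". The other rows cover concomitant vaccination, unsolicited symptoms and concomitant medication. There is no row for solicited local symptoms.

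**Tables affected.** These are the ones described in SAP 6.4.1 as "The percentage of subjects reporting each individual solicited local and general AE during the 8-day" follow-up, under a heading that presents them as the analyses the protocol planned.

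**Declared changes.** SAP section 9 describes the assay re-development and refers to 6.1.2, 6.3.2 and 6.4.2 for the rest. None of these mentions missing solicited data.

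**The concern.** The protocol separates events that are actively solicited on a diary card from events that are only known if reported. For the first, a missing card is missing data. For the second, silence is taken as absence. The SAP removes that separation for the individual solicited-symptom tables without saying so.

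Three things follow.

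- Each individual solicited rate can only be equal to or below the one the protocol prespecified, in a trial whose secondary objectives include the reactogenicity of the vaccine in pregnant women.
- If card return differs between groups, the dilution differs too, and the side-by-side rates shift for a reason unrelated to the vaccine.
- For pain, redness and swelling the SAP does not settle the rate. The text implies all dosed women, while the mock table for local symptoms (Template 19) defines N by documented doses. No documented-only analysis of local symptoms is specified in the text to fall back on.

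Tables that combine solicited and unsolicited symptoms are not affected, because the protocol itself counts non-reporters as event-free there.

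**Working it through.** **1. Reproduce the printed figures.** The only figures in the documents that show the denominator are the SAP's mock tables, copied from another study.

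- Template 17, symptom-sheet return: 330/335 = 98.5% and 329/336 = 97.9%. Both match.
- Template 19, any pain, documented doses, exact (Clopper-Pearson) 95% CI: 237/330 = 71.8% (66.6 to 76.6) and 248/329 = 75.4% (70.4 to 79.9). Both match.

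**2. Apply the SAP text to the same counts.** The numerator stays and the denominator becomes all dosed.

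- First group: 237/335 = 70.7% (65.6 to 75.6), a fall of 1.07 points.
- Second group: 248/336 = 73.8% (68.8 to 78.4), a fall of 1.57 points.

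**3. General formula.** Let p be the rate among women with a record and c the share of dosed women with a record. The protocol rule reports p. The SAP rule reports p × c. The fall is p × (1 − c), which is never negative.

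**4. Range for this trial.** The number dosed is taken as 340 per group (SAP Table 1). The return c is not given for this trial, so 98.5%, 95% and 90% are assumed, giving 335, 323 and 306 women with a record. Counts are rounded to whole women.

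| Symptom rate | Return | Protocol rule | SAP rule |
|---|---|---|---|
| About 70% | 98.5% | 234/335 = 69.9% | 234/340 = 68.8% |
| About 70% | 95% | 226/323 = 70.0% | 226/340 = 66.5% |
| About 70% | 90% | 214/306 = 69.9% | 214/340 = 62.9% |
| About 23% | 98.5% | 77/335 = 23.0% | 77/340 = 22.6% |
| About 23% | 95% | 74/323 = 22.9% | 74/340 = 21.8% |
| About 23% | 90% | 70/306 = 22.9% | 70/340 = 20.6% |
| About 10% | 98.5% | 34/335 = 10.1% | 34/340 = 10.0% |
| About 10% | 95% | 32/323 = 9.9% | 32/340 = 9.4% |
| About 10% | 90% | 31/306 = 10.1% | 31/340 = 9.1% |

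By formula, a 70% symptom falls by 0.70 × 0.015 = 1.05, 0.70 × 0.05 = 3.5 and 0.70 × 0.10 = 7.0 points. In the last case the exact 95% CI under the SAP rule is 57.6 to 68.1, which excludes the documented rate of 69.9%.

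**5. Unequal return.** Assume the same 30% rate among women with a record in both groups, with 5% of records missing in one group and 15% in the other. The SAP rule reports 0.30 × 0.95 = 28.5% against 0.30 × 0.85 = 25.5%, a 3-point difference produced by card return alone.

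**6. Is the change declared?** SAP 6.4.2 has five items: analysis by dose, infant unsolicited symptoms, the concomitant-medication window moving from 4 to 8 days, the SAE summary, and the household-contact set. The denominator for solicited symptoms is not among them. Since a change as small as the medication window is listed, the omission does not reflect a practice of listing only major changes.

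**The case against.** **The protocol's rate is not lost for general symptoms.** The SAP limits one of its rules to the analysis on administered doses, and the denominator table keeps completed screens as a sensitivity analysis. This stands for general symptoms. It does not remove the conflict: the opening paragraph of 11.2.5.1 and the whole of 11.2.6 carry no such limit, and nothing equivalent is stated for local symptoms.

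**Template 19 already uses documented doses for local symptoms, so a documented-only analysis exists; or, if templates do not count, the text governs and there is no ambiguity.** SAP section 12 calls the templates illustrative and subject to adaptation, so they cannot supply a planned analysis. On that reading the text governs, local symptoms go to all dosed women, and the departure from the protocol is complete. In practice a programmer has text and mock table pointing in different directions, with no table row to decide.

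**The effect is small and the endpoints are descriptive.** At the mock return of about 98% the shift is 1.1 to 1.6 points, against a CI of roughly 5 points either side. No test or success criterion depends on it. Protocol 5.6.1.3.9 requires unreturned cards to be chased. All of this stands and limits the weight of the point.

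**Documented-only is not proven unbiased.** This is also true. If symptom-free women return fewer cards, the protocol's rule overstates. The case rests on an undeclared replacement of the prespecified rule, not on that rule being free of bias.

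**Disclosure may still follow.** Protocol 10.10 requires changes to be described and justified in the study report. That does not excuse the omission from the SAP, and a change the SAP does not identify is easily overlooked later. The SAP also cites a protocol version, an administrative change of 06-SEP-2016, that is not among the documents. The protocol glossary confines administrative changes to logistical or administrative matters, so it is unlikely to have altered this rule, but that cannot be checked.

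**Conclusion.** The concern holds. As written, the SAP replaces the protocol's primary rule for individual solicited symptoms with one that gives equal or lower rates. It does not list the change, and it leaves local symptoms without a denominator row or a documented-only analysis.

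The size depends on diary return in this trial, which the documents do not give. At about 98% return, a common symptom moves by 1 to 1.6 points. The effect becomes material for common symptoms when return is near 90%. Rare symptoms barely move.

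The point is confined to secondary, descriptive reactogenicity endpoints. Combined tables, the cord-blood objective and the sample size are untouched. It should be fixed because the departure is undeclared and easily corrected.

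**What to change.** 1. In SAP 11.2.5.1 and 11.2.6, make women with a completed symptom screen for the dose in question the primary denominator for each individual solicited symptom, local and general.
2. Add a solicited local symptom row to the denominator table.
3. Keep the analysis of all dosed women, with missing counted as none, as the sensitivity analysis for both local and general symptoms.
4. Leave the combined solicited and unsolicited tables on all dosed women, as the protocol has them.
5. Make the text, the denominator table and Templates 19 and 20 agree. The two templates already use documented doses. Produce the Template 17 compliance table by group and by dose.

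If the sponsor prefers the SAP rule, list and justify it in section 9, bring Templates 19 and 20 into line, and add a documented-only analysis for local symptoms.

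The cost is some SAP wording, one table row and one extra sensitivity table for local symptoms. No new data are needed. Compared with the SAP as written, individual solicited rates would rise slightly and their intervals would widen marginally.
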